Several lines of evidence demonstrate that ketones are a preferred fuel for the brain, have neuroprotective effects, and may enhance neurocognitive function in various pathological or physiologically stressed states. At the low end of nutritional ketosis (0.5 mM), ~5% of whole brain energy metabolism is provided by ketones. At ketone concentrations of 1.5 mM (typical of KDs), ketones supply nearly 20%; at the higher end of nutritional ketosis 4-5 mM [achievable with ketone esters (KE)], half of the brain energy demands are met by ketones [18-20]. Importantly in situations where brain glucose metabolism is impaired, uptake and utilization of ketones remain fully intact [21], suggesting a hierarchy of importance placed on ketones as the preferred fuel for human brains. For example, when ketones are elevated in the circulation there is a remarkable protection from the adverse signs of hypoglycemia [16, 17].

RESEARCH OBJECTIVE

• Determine the degree to which short-term use of ketone esters (KEs) protects against fatigue from moderate sleep restriction and exercise.

Key outcome variables will include **5** major categories:

1) SLEEP OUTCOMES

- a) The sleeping protocol will be monitored by investigators and personnel with experience in sleep medicine. Participants will be required to reduce sleep by 50% of normal, for 4 consecutive nights, to observe potential deficits in physical and cognitive performance [22].
- b) Heart rate and sleep parameters (timing, duration, and quality of sleep) will be assessed by wrist-based acceleration with cloud technology (Polar Unite[™], Polar USA). This monitor is less burdensome than other sleep monitoring technologies and less likely to interfere with normal sleep and activity demands of the cadets. We have used this watch in our work with athlete tracking in sport science with reliable and valid results. Each participant will be fitted with the watch for acclimatization and then establish 3-day baseline patterns for 3 nights before the sleep loss protocol.
- c) Dietary standardization, including the same meals for all subjects and control of caffeine, will be implemented. Proper hydration will also be emphasized and evaluated at testing sessions via urine specific gravity.

2) EXERCISE PERFORMANCE

- a) Since weight training is now a crucial part of any warfighter's physical preparation, we will have subjects perform two weight training workouts emphasizing all major muscle groups on Days 2, 3 and 4.

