- b) Workouts will be supervised by trained personnel. All physical activity will be performed in our laboratory weight room located in the Physical Activity and Educational Services (PAES) Building ([name]).
- c) On Days 1 and 5, cognitive and physical tests and questionnaires (McGill Pain Questionnaire, the Shortened Profile of Mood States, and the Pittsburgh Sleep Quality Index) will be examined around the sleep restriction/exercise challenge. Time of day, eating, and activity will be strictly standardized the day prior to all assessments.

3) NEUROPSYCHOLOGICAL ASSESSMENTS

a) The first cognitive assessment will be done via *Automated Neuropsychological Assessment Metrics* (**ANAM**) (Department of Defense, [name]). This cognitive battery is a library of computer-based tests of domains including attention, concentration, reaction time, memory, processing speed, decisionmaking, and executive function. The ANAM core testing battery will be used, which assess of the following areas: participant information, sleepiness scale, symptoms checklist, mood scale, simple reaction time, code substitution- learning, procedural reaction time, mathematical processing, matching to sample, code substitutiondelayed, simple reaction time (repeated), and go no go.

- b) The second cognitive assessment will be delivered via Cambridge Neuropsychological Test Automated Battery (CANTAB). This iPad delivery assessment will include an Information Sampling Task to test impulsivity and decision making, response time (in msec), which provides a level of sensitivity not available with traditional paper and pencil tasks, processing speed, executive functioning, and spatial memory. We have also incorporated tasks which assess the ability to rapidly identify expressed facial emotions, which may index one's ability to accurately respond to overtly threatening or non-threatening stimuli.

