a) Continuous quantification of interstitial fluid glucose and beta-hydroxybutyrate (BHB) will be monitored using sensor-based devices developed and manufactured by Abbott Biowearables. The systems consist of three components: 1) a sensor that incorporates a subcutaneously implanted electrochemical glucose/ketone sensor and associated on-body electronics. 2) a disposable, sensor application device, which is used to adhere the sensor to the skin of the user and to insert the sensor tail just below the surface of the skin. And 3) a handheld device (reader or phone app) which activates the sensor by near-field communication and continuously obtains glucose and BHB readings at one-minute intervals from the sensor via Bluetooth short-range wireless communication. A separate sensor will be used for glucose and BHB monitoring. Sensor values will be blinded to the participant and research personnel such that the reader (or phone) only displays whether or not the matching sensor is functional or not. Glucose and BHB sensor data is therefore not accessible for medical or non-medical decision-making. Readers (or Phones), sensors, and Patch Delivery Units are uniquely identifiable through individual serial numbers. Readers (or Phones) require periodic charging

with a power chord (at least weekly). Sensors do not require charging. The wear period for a sensor is 14-days and thus we will have participants apply new sensors during the second cross-over period after the 14-day washout period. Sensors will be placed on the non-dominant arm (mid-triceps region) during each experimental phase.

b) Fasting venous blood will be collected at baseline and on Day 1 and Day 5 of the sleep restriction protocol to measure metabolites and hormones in serum and plasma. Participants will be exposed to a maximum of 4 blood draws during the entire study.

METHODS

Experimental Approach.

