We will conduct a double-blind, placebo-controlled, two-period cross-over study (**Figure 1**). The order of treatment will be balanced (i.e., half start with KE and half start with Placebo). Participants (n = 60) will be familiarized with all the physical performance tests to minimize learning effects and undergo baseline assessments. Subjects will then be randomized to either the KE or Placebo condition. On the morning of Day 1, prior to administration of KE or Placebo, subjects will undergo Pre-Testing inclusive of a blood draw, physical, and cognitive performance. For that night, and the next 4 nights, all subjects will restrict their sleep by 50%. On the morning of Day 5, the same testing battery performed on Day 1 will be replicated. KE or Placebo ingestion will occur on Days 2, 3, and 4 (2 doses/day), and include 1 dose on Day 5. After a 2-wk washout period, during which time participants return to their normal sleep and exercise habits, they will replicate the exact same 5-day protocol except they will receive the opposite treatment.

[figure not shown]

Figure 1 | Experimental Design

Rationale for Design.

We expect to show that short-term sleep restriction combined with physical exertion is associated with disturbed glucose metabolism as well as impaired cognitive function and physical performance. Based on emerging animal and human evidence indicating that ketosis is associated with enhanced cognition and improved physiological tolerance and performance in response to physical exertion [25, 26], our central **hypothesis** is that KE ingestion will lessen the detrimental effects of sleep restriction on cognitive and physical performance. This will be the first work to specifically explore how ketosis impacts cognition in the context of sleep restriction and performance tasks.

Participants.

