Participants that meet the initial qualifying criteria will visit the study center for a screening meeting. The participant and a member of the research team will meet in a private office to discuss the informed consent form. The informed consent form will be provided to the participant for their review, the study will be described in full detail and any questions the interested participant has will be encouraged and responded to. If they choose to participate in the study, they will be asked to sign the consent form providing written consent. The participant will be informed that even though they signed the consent form, their participation in the study is dependent on the results of their questionnaires to determine if they meet the study criteria. If the participant provides consent, they will be provided with a few questionnaires including medical history, physical activity history, a menstrual history for women, a food frequency questionnaire, and a gastrointestinal health status questionnaire. All collected samples will be coded to maintain participant anonymity. We will also measure height, weight. Participants will receive a call from one of the study personnel within days of the screening visit to inform them if they are eligible or not and will provide the participants with their results from the screening visit. If the participant is eligible for the study and is still interested in participating, then he/she will be scheduled to return to the study center for baseline testing.

Testing Sessions.

A schedule of the testing battery for the 5-day sleep restriction protocol is provided in **Figure 2**. The familiarization meeting will describe all the protocols in greater detail to accustom participants to their study duties and minimize training learning effects, followed by 5, consecutive, in-person testing sessions. Days 1 and 5 comprise primarily of blood assessment, cognitive testing, virtual simulator shooting, and power/reaction time test. Days 2, 3, and 4.

	Blood Draw	HR Monitoring	CGM/CKM	Cognitive Tests	Surveys	VirTra	Power/RT
Familiarization		х	х	х	х	Х	х
Day 1	х	х	х	х	х	Х	х
Day 2		х	х				
Day 3		х	х				
Day 4		х	х				
Day 5	х	х	Х	Х	Х	х	Х

Table 1 | Experimental Checklist.

HR, heart rate; CGM/CKM, continuous glucose/ketone monitoring; VirTra, Virtual Training; RT, reaction time.

[figure not shown]

Figure 2 | Experimental Timeline During Sleep Deprivation Protocol.

Familiarization:

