- 1. The primary goal is to fit each eligible participant with a wrist-based HR monitor and a CGM/CKM device (Abbott Freestyle Libre) within one week of the Day 1 visit. This familiarization protocol is intended to capture a week of free-living data and one week of each experimental condition.
 - a. Because we expect healthy, young adults, we don't anticipate screening for familiarization blood draw values. However, each consented participant will be given the opportunity to have their blood drawn by a trained phlebotomist if they have reservations about their blood values (e.g., metabolic panel, lipid panel) but still wish to participate in the study.
- 2. A secondary goal is to present the participants with each of the testing duties during the study, such as surveys, computer/iPad assessments, virtual shooting scenarios, how to squat jump on a force plate, and Quick Board reaction time.
- 3. Lab members will conduct a presentation of proper weightlifting lifting and running form expected during training days to minimize exposure to injury.

Test Day 1 & 5:

- 1. Participants will arrive at the testing lab ([name]) between 6:00-9:00h, hydrated and after an overnight fast (<8h).
- 2. *Blood Draws:* After 10 minutes of rest, a trained phlebotomist will perform an intravenous blood draw from the antecubital fossa using a 21G butterfly needle. Total blood collected will be limited to two test tubes (total volume 2 x 10mL): EDTA plasma and serum.
- 3. Supplement Ingestion: The first supplement dose (either KE or PL) will be consumed before commencing the cognitive testing battery.
- 4. *Cognitive Tests:* A series of computer and iPad-based cognitive tests will be administered to each participant to measure their attention, information processing, memory, function, inhibition, and social and emotional domains.
- 5. *Surveys:* A secondary assessment of well-being will be administered in the form of questionnaires: McGill Pain Questionnaire, the Shortened Profile of Mood States, and the Pittsburgh Sleep Quality Index.
- 6. VirTra: Participants will be tested on shooting competency using compressed gas weapons. The system is designed to record each weapon action (pistol/rifle) and simulate bullet trajectory and recoil without firing an actual projectile (i.e. bullet). Measures of reaction time, accuracy, precision, and spread will be recorded by a trained team member present in the room.

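### The fast before the Day 1 and Day 5 blood draws is printed as a ceiling of under 8 h with no minimum, which does not fit the fasting samples the protocol calls for; the inequality is probably reversed

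*Protocol*

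**What the plan says.** Study Procedures, Test Day 1 & 5, item 1, sets the condition for the blood draw that follows in item 2: participants arrive "between 6:00-9:00h, hydrated and after an overnight fast (<8h"). This is the only place in the readable protocol that gives the fast a duration.

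Research Objective, 5) Blood Biomarkers, item b, states what the samples are meant to be: "Fasting venous blood will be collected at baseline and on Day 1 and Day 5 of the sleep restriction protocol", for metabolites and hormones. The same item adds: "Participants will be exposed to a maximum of 4 blood draws during the entire study".

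Two other places bear on intake before testing:
- Sleep Outcomes, item c: "Dietary standardization, including the same meals for all subjects and control of caffeine, will be implemented".
- Exercise Performance, item c: "Time of day, eating, and activity will be strictly standardized the day prior to all assessments".

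Under Methods, Experimental Approach, the Day 1 draw comes before dosing ("prior to administration of KE or Placebo, subjects will undergo Pre-Testing inclusive of a blood draw"), and in the second period participants "they will replicate the exact same 5-day protocol except they will receive the opposite treatment". The table headed "Table 1 | Experimental Checklist" marks blood draws on Day 1 and Day 5 only. Familiarization, item 1a, offers every consented participant an optional draw if they are uneasy about their blood values.

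**The concern.** A fasting requirement normally sets a floor, so that a sample is not taken soon after food. The printed text sets a ceiling instead. It admits very short fasts and puts fasts of 8 h or more out of specification. It also fits poorly with the word overnight in its own sentence and with the fasting samples called for under Blood Biomarkers.

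Blood biomarkers are one of the five key outcome categories, and metabolites and hormones can depend on time since food. Sleep is restricted before Day 5 but not before Day 1. Without a stated minimum, fasting time could differ between the two days and become mixed into the Day 1 to Day 5 change.

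A lesser matter is the draw count: the stated maximum leaves no room for the optional draw.

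**Working it through.** **Inputs**
- Arrival window 6:00 to 9:00h, and a fast of less than 8 h (Test Day 1 & 5, item 1).
- Restricted-sleep examples with a 3am bedtime (Test Day 1 & 5, item 9).
- Draw days 1 and 5 (Table 1); two periods (Experimental Approach); stated maximum of 4 draws (Blood Biomarkers, item b).
- Assumption, for illustration only: an ordinary last meal between 18:00 and 21:00. The protocol gives no meal times.

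**1. The rule as printed.** Last intake must be later than arrival minus 8 h.
- 6:00 - 8 h = 22:00 the evening before.
- 9:00 - 8 h = 01:00 the same morning.

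So intake must fall after 22:00 to after 01:00, depending on arrival. Nothing sets how long before arrival it must stop.

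**2. An ordinary overnight fast against that rule**, under the assumed meal times.
- Shortest: 21:00 to 6:00 = 9 h.
- Longest: 18:00 to 9:00 = 15 h.

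Every value from 9 to 15 h exceeds 8 h, so each such participant would be outside the literal rule.

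**3. Whether anything else supplies a floor.**
- The items on standardized meals and on eating the day before give no hours.
- Sleep does not supply one on Day 5: from a 3am bedtime to the arrival window is 3 h (6:00) to 6 h (9:00).

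**4. Whether the sign could be a PDF reading error.** Inequality signs read sensibly elsewhere: the 7-hour sleep target in the Background, the age and BMI exclusions, and the time to ketosis under Supplementation. A misreading is therefore unlikely, though not fully excluded.

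**5. Draw count.**
- Scheduled: 2 days x 2 periods = 4, which reproduces the stated maximum exactly.
- With the optional familiarization draw: 4 + 1 = 5.
- If the baseline sample in Blood Biomarkers is separate from Day 1, the total including the optional draw is 4 + 1 + 1 = 6 (one baseline in all) or 4 + 2 + 1 = 7 (one per period). The protocol does not settle whether it is separate.

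**The case against.** The strongest reply is that this is a one-character slip whose intent is plain. The sentence speaks of an overnight fast, the biomarker section calls for fasting blood, and eating and time of day are standardized before assessments. A fast just short of 8 h may still give a usable fasting sample, so the two sections are in tension rather than flatly opposed. Figure 2, the experimental timeline, is not shown and may carry timing detail. Data analysis specifies only cognitive scores, and glucose is also monitored continuously.

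Most of this stands and keeps the point minor. It does not remove it: the wrong threshold sits in the operative procedure for the draw, and no readable text gives the right one.

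Four stronger readings are tempting and are not supported:
- *Properly fasted participants would be turned away.* The protocol does not say how staff would act, and a rule that excludes ordinary overnight fasts might simply be recognised as a slip.
- *The Day 1 versus Day 5 difference in fasting time is at most 3 to 4 h*, from the sleep examples (6 h to 3 h, 8 h to 4 h). That presumes eating until bedtime on both days and a draw at waking. The assumed meal times in step 2 alone allow 15 - 9 = 6 h between two visits, while identical meal and arrival times give 0 h.
- *The treatment comparison is biased.* The rule and schedule are the same in both periods, so the wording favours neither treatment.
- *The baseline sample is simply the Day 1 draw.* Experimental Approach places baseline assessments before randomization, and Screening schedules a return visit for baseline testing. Table 1 shows no blood draw at familiarization. The text points both ways.

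**Conclusion.** The point holds as a minor error in a stated threshold. As printed, the fast is a maximum without a minimum and is inconsistent with the fasting samples the protocol asks for. That the inequality is reversed is an inference, a probable one; the intended figure is not in the document. The clock limits of 22:00 and 01:00 follow directly from the printed rule. The 9 to 15 h range rests on the assumed meal times.

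The effect is limited to the blood biomarkers and their Day 1 to Day 5 change. Its size cannot be derived from the protocol and may be small, given the standardization of meals, eating and time of day. The ketone ester versus placebo contrast, the cognitive analysis and the sample size are not affected.

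The draw count is a wording inconsistency with no analytic effect: 4 scheduled draws fill a maximum of 4, and the optional draw would be a fifth.

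**What to change.** - The sponsor should reconcile Test Day 1 & 5, item 1, with Blood Biomarkers, item b, by restating the fast as a minimum duration. The figure should be the sponsor's own intended one, applied identically at all four Day 1 and Day 5 draws.
- Optionally, record the time of last intake at each of the four visits, so that any Day 1 to Day 5 difference in fasting time can be seen.
- Reconcile the maximum number of draws with the optional familiarization draw, by including it or expressly excluding it, and state whether the baseline sample is separate from Day 1.

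The cost is a few wording corrections and, if the option is taken, one clock time per draw visit.

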Participants will be recruited through posted flyers, e-mails, word of mouth, and by using ResearchMatch through the OSU CCTS. Print and email advertisements will instruct interested individuals to call the study center ([name] Lab, Kinesiology Program) for additional information about the study. Participants may either respond to the email address to set up a phone call or may call during the phone-in hours. One of the key personnel involved in the project will describe the study and determine preliminary qualifications by conducting a scripted phone interview. Participant answers to qualifying criteria questions will be recorded to assess whether or not the person calling meets the initial qualifying criteria. If it is determined that the interested participant does meet the initial qualifying criteria, an appointment will be made for the interested participant to visit the study center for a screening meeting.

Supplementation.

The ketone ester (KE) supplement we plan to use the C6 Diester (Metabolic Switch), which delivers rapid (<30-min) and sustained (~5-hr) ketosis in a predictable and dosedependent manner. We have used this particular KE in previous studies at OSU (e.g., protocol number 2020H0005 and 2021HO425) and it is well tolerated and consistently elevates ketones into the desired range. Metabolic Switch and Placebo will be provided in a flavor and volume matched single serving nondescript plastic container in the morning prior to testing on Days 1 and 5, and then again in the evening during the sleep restriction period. The product will be consumed twice per day: once in the morning and once in the evening. Product will be distributed in a blinded manner by people not involved with testing. For more details regarding the supplement refer to *Supplementation* section below.

C6 Diester and finished product (Metabolic Switch) is manufactured under good manufacturing practice conditions for BHB Therapeutics Ltd (and its parent company, Juvenescence Ltd). BHB Therapeutics conducted a program of safety and efficacy testing

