This will be the first prospective study to compare responses between a group that receives a ketogenic diet and/or ketone supplements to a group that receives the same treatment undergoing a placebo. Statistical analyses will occur in collaboration with the OSU Center for Biostatistics. For data reduction purposes, z-scores within a given cognitive domain will be averaged to generate a composite measure for that domain. Prevs. post-stressor differences in the composite cognitive score will be calculated and summarized for all subjects across treatment arms and time points. Differences in cognitive scores between treatment arms will be analyzed using two-way repeated-measures ANOVA. An interaction term between time and treatment will test whether there was any carry-over effect. Normality and heteroscedasticity will be checked using residual plots. Sample size calculations were based on a randomized crossover design of male athletes, which found an effect size of 0.7 in pre- vs. post-test cognitive performance between placebo and KE [32]. Our sample size of 60 subjects has 96.5% power (α =0.05) to detect this effect size (standardized mean difference) between treatments.

REFERENCES

- 1. Shattuck, N.L., et al., *The role of sleep in human performance and well-being*. 2020, Oxford University Press.
- 2. 2019 Health of The Force. U.S. Army Public Health Center.
- 3. Fullagar, H.H., et al., Sleep and athletic performance: the effects of sleep loss on exercise performance, and physiological and cognitive responses to exercise. 2015. **45**(2): p. 161-186.
- 4. Belenky, G., et al., *Patterns of performance degradation and restoration during sleep restriction and subsequent recovery: A sleep dose-response study.* 2003. **12**(1): p. 1-12.
- 5. Smith, C.D., et al., *Sleep restriction and cognitive load affect performance on a simulated marksmanship task.* 2019. **28**(3): p. e12637.
- 6. Broussard, J.L., et al., *Impaired insulin signaling in human adipocytes after experimental sleep restriction: a randomized, crossover study.* 2012. **157**(8): p. 549-557.
- Hanlon, E.C. and E.J.P.o.t.N.A.o.S. Van Cauter, *Quantification of sleep behavior and of its impact on the cross-talk between the brain and peripheral metabolism.* 2011.
 108(Supplement 3): p. 15609-15616.
- 8. Spiegel, K., R. Leproult, and E.J.T.I. Van Cauter, *Impact of sleep debt on metabolic and endocrine function*. 1999. **354**(9188): p. 1435-1439.

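### The protocol places the Day 1 cognitive tests both before and after the first dose, so the pre-test score is either untreated or on-treatment

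*Protocol*

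**What the plan says.** Three places in the protocol fix when product is taken relative to testing.

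- **Methods, Experimental Approach.** The sentence on the first test morning reads: "prior to administration of KE or Placebo, subjects will undergo Pre-Testing inclusive of a blood draw, physical, and cognitive performance". The dosing schedule follows: "KE or Placebo ingestion will occur on Days 2, 3, and 4 (2 doses/day), and include 1 dose on Day 5". No Day 1 dose is listed.
- **Supplementation.** Product is provided "in the morning prior to testing on Days 1 and 5, and then again in the evening during the sleep restriction period". The same paragraph adds: "The product will be consumed twice per day: once in the morning and once in the evening".
- **Study Procedures, Test Day 1 & 5.** Item 2 is the blood draw. Item 3 reads: "The first supplement dose (either KE or PL) will be consumed before commencing the cognitive testing battery". Item 4 is the cognitive battery; surveys, marksmanship, force plate and response time follow as items 5 to 8.

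Two further statements give the order its weight. Supplementation says the product "delivers rapid (<30-min) and sustained (~5-hr) ketosis". Data analysis says that pre- versus "post-stressor differences in the composite cognitive score will be calculated and summarized for all subjects across treatment arms and time points".

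**The concern.** Day 1 is the pre-stressor measurement in each period and Day 5 the post-stressor one. Whether Day 1 is dosed decides what the change score estimates.

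- **Undosed Day 1.** The KE-minus-placebo difference in change is the whole effect of KE on Day 5, measured against an untreated baseline.
- **Dosed Day 1.** Any acute KE effect common to both days cancels. What remains is the effect on Day 5 beyond that on Day 1, which is added protection under sleep restriction.

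The stated hypothesis, that "KE ingestion will lessen the detrimental effects of sleep restriction on cognitive and physical performance", can be read as either. Both quantities are defensible, but they are different, and the protocol prescribes a sequence for each. Staff who work from the step-by-step procedure will obtain an on-treatment pre score, while a reader of the design section will take it to be untreated. If the order varied between participants or periods, the estimate would mix the two. The marksmanship, jump and response-time baselines are affected in the same way. The Day 1 fasting blood is not, because it precedes the dose under either order.

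**Working it through.** **The sequences side by side**

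| | Experimental Approach | Supplementation and Test Day 1 & 5 |
|---|---|---|
| Day 1 blood | before product | before product |
| Day 1 cognitive and physical tests | before product | after the first dose |
| Day 1 dose | none listed | morning, possibly evening |
| Doses per period | 2 × 3 + 1 = 7 | 7 + 1 = 8, or 7 + 2 = 9 (inferred; no total is stated) |

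**Inputs for the size.** From Data analysis: standardised effect 0.7, n = 60, α = 0.05, stated power 96.5%. I take α as two-sided, since the protocol does not say. The share f of the 0.7 effect already present in a dosed Day 1 score is not in the document, so it is an assumption shown over a range.

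**Reproducing the stated power.** A noncentral t with noncentrality (0.7/√2) × √60 = 3.83 and 58 degrees of freedom gives 96.5%, which matches. If 0.7 is instead standardised by the SD of the within-subject difference, the noncentrality is 0.7 × √60 = 5.42 with 59 degrees of freedom, and power is 99.96%. Both bases are carried below.

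**Change contrast.** With effect 0.7 on Day 5 and 0.7f on a dosed Day 1, the difference in change is 0.7 − 0.7f = 0.7(1 − f).

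| f | Contrast | Power, basis matching the protocol | Power, paired basis |
|---|---|---|---|
| 0 | 0.70 | 96.5% | 99.96% |
| 0.25 | 0.525 | 80.7% | 97.9% |
| 0.50 | 0.35 | 47.0% | 76.0% |

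**Mixed execution.** If half of the KE Day 1 sessions were dosed first and f = 0.50, the contrast is 0.7 × (1 − 0.5 × 0.5) = 0.525, with power 80.7% or 97.9%.

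**Treatment main effect instead.** If the test is the average over both days, the contrast is (0.7 + 0.7f)/2 = 0.7(1 + f)/2. This gives 0.35, 0.4375 and 0.525 for f = 0, 0.25 and 0.50. Holding the SD as above, power on the basis matching the protocol is 47.0% at f = 0 and 80.7% at f = 0.50, so here a dosed Day 1 raises power. Holding the SD is a simplification, because a change score and a two-day average need not have the same SD.

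**The case against.** The strongest case on the other side accepts the contradiction and disputes its weight.

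- **The power loss depends on which test is meant.** Data analysis says the pre-post differences are calculated and summarised. The named test is a two-way repeated-measures ANOVA of cognitive scores between arms, with the time-by-treatment interaction assigned to carry-over. Under a main-effect reading a dosed Day 1 helps. This stands: the loss is specific to the change contrast, and f is unknown.
- **Validity survives either order.** Treatment is randomised within subject, so Day 5 KE versus placebo is not biased by this issue. That is correct, but it does not say what the change score measures.
- **Mixed execution is speculative.** Nothing suggests that one team would vary the order, and the one-minute ketone sensor record could show afterwards whether a KE session was dosed, if test times are kept. This is fair, and mixed execution is a secondary risk. A sensor record would identify a dosed baseline but could not restore an undosed one.
- **An undosed session already exists.** Cognitive and performance tests are scheduled at familiarisation. That session is partly practice and precedes only the first period, so it cannot replace a baseline in each period.
- **The text may be looser than it looks.** The Supplementation wording could describe dispensing, and item 3 could be a shared template meant for Day 5. But item 3 says the product is consumed, and calls it the first dose. Under the design schedule six doses precede Day 5, so the first dose of the period cannot fall there. Figure 2 might show the intended order, but it is not available here and would not remove the conflicting sentences.

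**Conclusion.** The concern holds. The current text gives two incompatible sequences for Day 1, and with them 7 versus an inferred 8 to 9 doses per period. This needs no assumption beyond the quoted sentences. It must be settled in the protocol, because it governs when product is given and a baseline taken after dosing cannot be recovered.

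The effect on power is conditional. It assumes that the change contrast is the test and that f is above zero. Over f = 0 to 0.50, power runs from 96.5% down to 47% on the basis that matches the protocol, and from 99.96% down to 76% on a paired basis. It runs the other way if the treatment main effect is the test. The case for correction therefore rests on the meaning of the pre value, not on a demonstrated loss of power.

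**What to change.** Preferred: amend Supplementation and Test Day 1 & 5, item 3, to agree with Experimental Approach. State that no product is taken until every Day 1 test in that period is complete, that the dose before testing applies to Day 5 only, and that one dose count applies per period. Under the Experimental Approach schedule that count is 7, with no Day 1 evening dose.

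If a dose before the Day 1 tests is intended, amend Experimental Approach instead and stop treating Day 1 as an untreated value. Then compare Day 5 scores directly between treatments for the total KE effect, and keep Day 5 minus Day 1 only as the estimate of added protection under sleep restriction.

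Either route costs a wording amendment and adds no procedures, visits or participants.
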